7.2.2.2. Seroprevalence

Seroprevalence will be summarized at visit 1 with the demography characteristics.

7.3. Analysis of symptoms and spectrum of dengue disease

7.3.1. Analysis as planned per protocol

The clinical characteristics of symptomatic dengue infection (symptoms, hospitalizations, severity) will be presented.

The analyses will be performed on the ATP cohort.

7.3.2. Additional considerations

The following parameters will be accounted in the summary:

- Laboratory diagnosis (PCR confirmed, other serologically confirmed, negative, inapparent, undetermined)
- Laboratory schedule (Early/Late)
- Primary dengue diagnosis (Yes/No/missing)
- Clinical diagnosis including severity and hospitalization

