4.2. Secondary endpoints

- DENV-type specific primary laboratory-confirmed symptomatic dengue infection.
- DENV-type specific secondary laboratory-confirmed symptomatic dengue infection.
- Primary symptomatic dengue infection (including laboratory-confirmed and probable cases).
- Secondary symptomatic dengue infection (including laboratory-confirmed and probable cases).
- Previous dengue infection(s) (dengue seroprevalence) at baseline.
- Primary inapparent dengue infection.
- Severity of symptoms of symptomatic dengue (using the 2009 WHO guidelines).

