6.2. Laboratory-confirmed symptomatic dengue case

Early presenter:

At least one of the following findings must be met for a laboratory-confirmed dengue case:

- Dengue virus identification through RT-qPCR on the acute serum sample
- Dengue virus NS1 positive on acute serum sample through ELISA.
- Anti-dengue IgM seroconversion between acute and convalescent serum samples through ELISA.

Late presenter:

- Anti-dengue IgM seroconversion between acute and convalescent serum samples through ELISA.

Acute and convalescent serum samples are samples taken at the first and follow-up visits for suspected dengue case, respectively.

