6.4. Probable dengue case

- For early presenters, a probable case will be that case without laboratory confirmation, presenting IgG positive in the convalescent sample.
- For late presenters, a probable case will be the case without seroconversion of IgM, presenting at least one IgG positive in one sample (acute or convalescent).

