6.6. Indeterminate dengue case

An indeterminate dengue case is a participant evaluated as an SDC (Section 6.1) and not classified as laboratory confirmed case (Section 6.2), probable case (Section 6.4) or negative case (Section 6.5).

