10. CHANGES FROM PLANNED ANALYSES

The definitions of laboratory-confirmed, probable, negative, indeterminate, primary and secondary symptomatic dengue cases were clarified.

The cohorts were clarified and the Total cohort without subjects with code 900 was added.

Some tables for the analysis of demographics will be performed on ATP cohort.

The computation of incidence rates was clarified. Incidences rates will also be performed on calendar year.

The statistical methodology to estimate the CI for proportions and incidence rates accounting for clustering effect will not use stratification by center for the analyses on overall centers (refer to Section 12.1).

The clinical characteristics of symptomatic dengue infection (symptoms, hospitalizations, severity) will be presented by dengue classification (lab-confirmed, probable, indeterminate or negative) and not by DENV type (DENV 1-4), study site, gender and age category.

Due to study termination:

- The interim analysis planned in the protocol was not done
- Tertiary objectives will not be analysed
- The following laboratory tests will not be performed:
 - Dengue 1-4 Neutralizing assay
 - Yellow Fever Neutralizing assay

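### SAP Amendment 1 section 7.3.2 has no class for probable cases in the clinical-spectrum summary, and the SAP's own definitions bar them from every class it lists

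*SAP*

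**What the plan says.** All references are to SAP Amendment 1 unless stated otherwise.

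- Section 7.3.1 has the clinical characteristics of symptomatic dengue infection presented on the ATP cohort. Section 7.3.2 names the parameters, the first being "Laboratory diagnosis (PCR confirmed, other serologically confirmed, negative, inapparent, undetermined". The others are early or late presentation, primary dengue diagnosis (yes, no or missing), and clinical diagnosis with severity and hospitalisation.
- Section 6.2 confirms an early presenter by RT-qPCR, by "Dengue virus NS1 positive on acute serum sample through ELISA", or by IgM seroconversion. A late presenter is confirmed by IgM seroconversion only.
- Section 6.4 defines the probable class in two parts: "For early presenters, a probable case will be that case without laboratory confirmation, presenting IgG positive in the convalescent sample", and "For late presenters, a probable case will be the case without seroconversion of IgM, presenting at least one IgG positive in one sample".
- Section 6.6 makes indeterminate the residual class, for suspected cases "not classified as laboratory confirmed case (Section 6.2), probable case (Section 6.4) or negative case (Section 6.5".
- Section 4.2 keeps "Primary symptomatic dengue infection (including laboratory-confirmed and probable cases" as a secondary endpoint, with its counterpart for secondary infection, and lists severity of symptoms of symptomatic dengue as another.
- Section 1 numbers six changes made by Amendment 1. None concerns the laboratory classes. Section 10 says that changes appear in the additional-considerations sections, 7.3.2 among them, and are also summarised in section 1.

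**The concern.** Section 7.3.2 gives a list of classes that differs from the classification in section 6 and does not say how one maps to the other. The probable class is missing. It is part of what the SAP calls symptomatic dengue, and the summary in 7.3 is meant to describe symptomatic dengue.

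At stake is the table that serves the severity endpoint. Suppose probable cases are dropped: the table then describes confirmed dengue only. If they are merged with confirmed cases, the confirmed rows hold cases that section 6.4 calls unconfirmed. If they go under *undetermined*, cases that count as dengue in the secondary endpoints share a row with cases that do not. The text does not say which will happen.

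**Working it through.** The plan gives no figure to reproduce here. The check sets the 7.3.2 list against section 6, then counts how often the two disagree.

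**Step 1. Can a probable case sit in any listed row?**

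| Row in 7.3.2 | Governing section | Probable case admitted? |
|---|---|---|
| PCR confirmed | 6.2, 6.3 | No. An early probable case has no laboratory confirmation; late presenters have no RT-qPCR |
| Other serologically confirmed | 6.2, 6.4 | No. Early: no confirmation. Late: no IgM seroconversion, which is the only late route |
| Negative | 6.5 | No. All planned tests must be negative, and a probable case has a positive IgG |
| Inapparent | 6.9 | No. It requires no clinical suspicion, and a probable case is a suspected case |
| Undetermined | none; nearest is 6.6 | No, if it means indeterminate. Section 6.6 excludes probable cases by name |

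**Step 2. Count the test patterns.** The inputs are the tests in the results table of SAP section 7, each positive or negative, with none missing.

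Early presenters (RT-qPCR, NS1, acute IgM, convalescent IgM, convalescent IgG), 2^5 = 32 patterns:

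- RT-qPCR positive: 2^4 = 16.
- RT-qPCR negative, NS1 positive: 2^3 = 8. Two of these also show IgM seroconversion; 6 rest on NS1 alone.
- Both negative, IgM seroconversion: 1 IgM pattern × 2 IgG results = 2.
- Confirmed: 16 + 8 + 2 = 26.
- The other 6 (3 IgM patterns × 2 IgG results): 3 probable, 1 negative, 2 indeterminate.

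Late presenters (NS1, acute and convalescent IgM, acute and convalescent IgG), 2^5 = 32 patterns:

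- IgM seroconversion: 2 × 1 × 4 = 8 confirmed.
- No seroconversion, at least one positive IgG: 2 × 3 × 3 = 18 probable.
- No seroconversion, both IgG negative: 2 × 3 × 1 = 6, of which 1 negative and 5 indeterminate.

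Section 6 gives each of the 64 patterns exactly one class. The probable patterns, 3 + 18 = 21, have no row in 7.3.2. Protocol Amendment 4 dropped NS1 for late presenters. Without it the late count halves to 16 patterns (4 confirmed, 9 probable, 1 negative, 2 indeterminate), so the gap does not depend on that test.

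**Step 3. The NS1 label.** The 6 early patterns that rest on NS1 alone fit *other serologically confirmed* only if that means confirmed by any test other than RT-qPCR. Protocol Table 9 lists NS1 under virology, while IgM and IgG are in Table 8 under humoral immunity. The SAP also expects NS1 results for late presenters, where they confirm nothing. Late patterns with NS1 positive and no IgM seroconversion number 1 × 3 × 4 = 12 (9 probable, 3 indeterminate). A loose reading of the row could take them in.

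**Step 4. Consistency within 7.3.2.** Primary dengue diagnosis is a parameter in the same list. Section 6.7 defines a primary case as confirmed or probable. One item of the summary therefore includes probable cases, and another has no row for them.

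**The case against.** The strongest objection is that 7.3.2 lists parameters and is not a table shell. The layouts are in the separate tables document, which is not available here. Amendment 1 section 9.1 cites the version dated 14 June 2019. The superseded SAP of that date said in its section 10 that the clinical characteristics "will be presented by dengue classification (lab-confirmed, probable, indeterminate or negative". The shells may therefore still carry a probable row. Section 6.4 still defines the class, so it can be derived case by case. All analyses are descriptive, and neither the primary endpoint nor the planned confirmed-or-probable incidence rates use the 7.3.2 labels. A difference from the superseded SAP is not itself an error, and 7.3.2 is one of the places where section 10 says changes are recorded.

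All of that stands, and it limits the effect. It does not put the probable class into the governing text, which conflicts with section 6 as written.

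A reader might infer four stronger points, which the documents do not support:

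- *NS1-confirmed cases have no row.* NS1 is an ELISA on serum, and directly after the PCR row the next label can be read as the rest of the confirmed class. This is an ambiguous label, not a proven gap.
- *Every dengue case beyond the 10 confirmed by RT-qPCR depends on faulty classes.* Cases confirmed by IgM seroconversion fit the second row exactly.
- *The severity of confirmed-or-probable dengue cannot be rebuilt, and undetermined does mix counted with uncounted cases.* Neither can be shown without the shells, and section 6.6 forbids the mixing if undetermined means indeterminate.
- *An inapparent row is an error.* Section 7.3 is headed as covering the spectrum of disease, so a separate row is defensible. It should only stay out of totals for symptomatic infection.

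**Conclusion.** The point holds for probable cases. The 7.3.2 list omits a class that the SAP counts as symptomatic dengue and that its definitions keep out of all five listed rows. Followed literally, the list drops or misclassifies these cases in the summary that serves the severity endpoint. Hospitalisation is affected too, as a descriptive item rather than part of that endpoint. Section 1 does not record the change. The NS1 label and the word *undetermined* are lesser faults of wording.

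The size in cases is unknown, because the documents give no number of probable or NS1-only cases. The 21 of 64 patterns show where the list fails, not how often. The conclusion assumes that section 6 governs classification and that *undetermined* means indeterminate. It should be corrected before the table is produced, but it does not touch the primary result.

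**What to change.** In section 7.3.2, replace the laboratory-diagnosis list with the section 6 classes:

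- laboratory-confirmed, with sub-rows for RT-qPCR; NS1 without RT-qPCR (early presenters only); and IgM seroconversion only;
- probable;
- negative;
- indeterminate, in place of *undetermined*.

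Add a confirmed-or-probable subtotal. On the early patterns above, the three sub-rows do not overlap and account for 16 + 8 + 2 = 26 confirmed. If inapparent infections are kept, show them as a separate row outside the symptomatic totals. Record the change in section 1, and check that the table shells match.

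The cost is one grouping variable and new row labels in one table. No new data are needed, since every class follows from results already listed in section 7.

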7.4. Analysis of tertiary objectives

Tertiary objectives will not be analysed.

7.5. Analysis of serious adverse events

Serious adverse events related to study procedures reported during the study period will be listed for all enrolled subjects.

8. ANALYSIS INTERPRETATION

All analyses are descriptive.

9. CONDUCT OF ANALYSES

9.1. Sequence of analyses

The planned interim analysis was not performed.

The final analysis will be performed when all prospective data have been collected and cleaned.

Study progress reports were generated during the study conduct to follow study progress using specified tables and using the study database as source data.

Description	Analysis ID	Disclosure Purpose (CTRS=public posting, SR=study report, internal)	Dry run review needed (Y/N)	Study Headline Summary (SHS) requiring expedited communication to upper management (Yes/No)	Reference for TFL
Final analysis	E1_01	SR, CTRS	No	Yes	Refer to EPI-DENGUE-006 BOD BR (116606) TFL (Final analysis) (14-JUN-2019).docx
Study progress reports	E1_02	Monitoring	No	No	Refer to EPI-DENGUE-006 BOD BR (116606) Additional Analysis Request E01_02 Study progress.docx

9.2. Statistical considerations for interim analyses

The planned interim analysis was not performed.

10. CHANGES FROM PLANNED ANALYSES

All changes are provided in the additional consideration sections [7.1.2](#), [7.2.2](#), [7.3.2](#), [7.4](#) and also summarized under section [1](#).

11. DATA DERIVATION RULES AND STATISTICAL METHODS

11.1. Data presentation

The following decimal description will be used for the analyses:

Display Table	Parameters	Number of decimal digits
Dengue cases	Incidence rate (in 1000 person-years) with LL & UL, person-years	1
Dengue cases	% of count, including LL & UL of CI	1
Dengue cases	Minimum, maximum, range	Number of decimals in the raw data
Dengue cases	Mean, median	Number of decimals in the raw data +1
Dengue cases	SD	Number of decimals in the raw data +2
Hematology/biochemistry	%	1
Demographic/baseline characteristics and changes between scheduled visits	Percentage, mean, median, standard deviation, minimum, maximum, Q1, Q3	1

CI = confidence interval

LL = lower limit of the confidence interval

SD = standard deviation

UL = upper limit of the confidence interval

Q1/Q3 = 25th and 75th percentiles

11.2. Handling missing data

No data handling will be performed in case of missing data.

11.3. Data derivation

11.3.1. Date derivation

Statistical Analysis Software (SAS date derived from a character date: in case day is missing, 15 is used. In case day and month are missing, 30 June is used.

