6.1. Suspected symptomatic dengue case

As per protocol a suspected symptomatic dengue case was defined by febrile illness with body temperature $\geq 38^{\circ}\text{C}$ measured (by any route) on at least two consecutive days and less than 14 days with or without the presence of other dengue symptoms or signs, without an obvious aetiology unrelated to dengue, based on investigator's judgement.

Note that few cases were reported as suspected symptomatic dengue cases without documentation of fevers. These cases will be ignored from all analyses on symptomatic dengue infections.

Although subjects are asked to come to a study hospital if fever (body temperature $\geq 38^{\circ}\text{C}$ by any route) is sustained for two consecutive days, a subject could present on the first day of fever. In this case the physician may still consider the subject as a suspected dengue case based on medical judgement and collect a blood sample for laboratory diagnosis.

A suspected dengue case presenting at the health care facility within 5 days following the onset of fever (i.e. day of fever onset and the next 4 days) is defined as an 'early presenter'.

A suspected dengue case presenting at the health care facility 6 days or more after the onset of fever will be defined as 'late presenters'.

An example of other signs and symptoms of dengue, associated with fever, include but are not limited to: fatigue, headache, pain behind the eyes, abdominal pain, nausea, vomiting, muscle ache, joint ache, diffuse rash on the trunk, abnormal sensitivity to light (photophobia) and itching of skin (pruritus).

The start date of a suspected symptomatic dengue case is defined by the date of fever or the date of first symptoms which ever appear last. In case both the date of fever and the date of first symptoms are missing, the start date will be the date of visit with symptoms.

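### Partial onset dates are filled with the 15th or 30 June without a check against the visit date, which can give an onset after the visit or turn an early presenter into a late one

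*SAP*

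**What the plan says.** SAP Amendment 1, section 11.3.1, gives one general rule for completing any date that was recorded as text: "in case day is missing, 15 is used. In case day and month are missing, 30 June is used". It sets no upper or lower bound. Section 11.2 adds nothing: "No data handling will be performed in case of missing data".

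Section 6.1 makes early or late status depend on the time from fever onset to presentation. Early means the onset day or one of the next four days. Late is "A suspected dengue case presenting at the health care facility 6 days or more after the onset of fever". The episode start is "the date of fever or the date of first symptoms which ever appear last". If both dates are missing, "the start date will be the date of visit with symptoms". Partial dates are not mentioned.

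Section 6.2 gives the two groups different case definitions. For early presenters, any one of three findings confirms: "Dengue virus identification through RT-qPCR on the acute serum sample", a positive NS1, or IgM seroconversion. For late presenters the only criterion is "Anti-dengue IgM seroconversion between acute and convalescent serum samples through ELISA". Section 6.3 defines virological confirmation by RT-qPCR with no early/late condition.

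Protocol section 5.7.1.1 stops considering subjects as suspected cases after day 30 of fever. Section 6.1 of SAP Amendment 1 has no such limit.

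**The concern.** Laboratory-confirmed symptomatic dengue is the primary endpoint, and whether an RT-qPCR or NS1 positive counts towards it depends on a lag in days. If the onset date is partial, that lag is computed from a day fixed in advance, without regard to the visit date that is on record.

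Three things could go wrong. A subject seen early in the month can be given an onset after the visit, which neither category in section 6.1 covers. A subject seen late in the month can be given an onset many days too early and be handled as late. And because section 6.1 takes the later of the fever and first-symptom dates, an imputed date that is too late overrides a complete, earlier one.

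**Working it through.** The plan states no figure that depends on this rule, so there is nothing to reproduce. The check follows the rule literally.

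**Inputs.** Imputed day 15, or 30 June if the month is also missing (11.3.1). Early = lag 0 to 4 days; late = lag 6 or more (6.1). A lag of 5 fits neither wording. Assumptions, not in the documents: onset uniform over a 30-day month, true lag uniform on 0 to 4 days, recorded month and year correct.

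**Formula.** Computed lag = visit date − imputed onset = (true onset day + true lag) − 15.

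**Two examples with the day missing.**
- Onset 22 March, visit 24 March, true lag 2. Imputed onset 15 March, computed lag 9: late.
- Onset 5 March, visit 7 March, true lag 2. Imputed onset 15 March, computed lag −8: onset after the visit.

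**Enumeration, day missing, true early presenters.** There are 30 onset days × 5 lags = 150 combinations.

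| Computed lag | Count for true lag 0, 1, 2, 3, 4 | Total | Share |
|---|---|---|---|
| below 0 (onset after visit) | 14, 13, 12, 11, 10 | 60 | 40.0% |
| 0 to 4 (early) | 5, 5, 5, 5, 5 | 25 | 16.7% |
| 5 (neither) | 1, 1, 1, 1, 1 | 5 | 3.3% |
| 6 or more (late) | 10, 11, 12, 13, 14 | 60 | 40.0% |

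Running over every actual visit date from 1 January 2015 to 31 December 2018 gives 39.4%, 16.4%, 3.3% and 40.9%. Errors also run the other way. Among true late presenters with lags of 5 to 29 days, 7.9% become early and 5.9% get an onset after the visit.

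**Day and month missing, true early presenters.** Over all visits in 2015 to 2018, 48.8% get an onset after the visit. For January to June visits in a non-leap year there are 181 × 5 = 905 combinations. In 10 of these the onset falls in the previous year, and in 5 the visit is on 30 June itself. That leaves 890/905 = 98.3% with an onset after the visit.

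**Effect on the calendar terms.** The model in section 7.2.2.1 uses year and month. With only the day missing, the recorded month and year are kept. With the month also missing, the year is kept but the fever date becomes 30 June, so the event is counted in June whenever that date sets the episode start.

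**Effect on confirmation.** A case re-derived as late stays laboratory-confirmed if IgM seroconverts. Otherwise section 6.4 makes it probable if IgG is positive in either sample; failing that, it is indeterminate. Section 6.3 would still call an RT-qPCR positive virologically confirmed, so 6.2 and 6.3 could disagree about the same case.

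**The case against.** The strongest reply is that the problem may never arise. Section 11.3.1 is a general date rule, and nothing shows that any fever-onset date is partial or that the eCRF accepts one. Subjects keep a daily temperature diary. At the visit, the choice of panel depends on whether the sample falls within 5 days of onset (Protocol Tables 12 and 13), so staff usually need the onset to the day. Section 7.3.2 lists early/late as a laboratory schedule, which suggests that status may come from the panel and not be recomputed from dates.

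This stands as a limit on size. It does not close the gap: section 6.1 reads as a derivation from dates, and its visit-date fallback shows that incomplete onset information was expected.

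A reader might infer more than the documents support:
- **That virologically positive cases are deleted from the primary endpoint.** This needs a partial date, status re-derived from it, and no IgM seroconversion.
- **That events move to the wrong year.** They do not. The month moves only under the 30 June branch.
- **That each switch costs 10% of confirmed cases.** The 10 in SAP section 1 are PCR-confirmed cases; the primary endpoint also counts NS1 and IgM confirmations.
- **That sections 11.2 and 11.3.1 conflict in substance.** Read literally they do, but this is mainly wording: one covers missing data, the other converts incomplete dates.

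**Conclusion.** The point holds as a gap in a derivation rule. Followed exactly, section 11.3.1 can produce an onset after the visit and can change the case definition that applies to a subject. Given a missing day, only about one in six true early presenters stays validly early; about 40% become late and about 40% get an onset after the visit. These shares rest on uniform onset dates and lags.

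The overall effect cannot be stated, because the number of partial onset dates is not given and may be small or zero. As an illustration only, suppose 1% to 10% of onset dates lacked the day. Of the 10 PCR-confirmed cases, the expected number moved to a lag of 5 or more would be 10 × 0.01 × 0.442 = 0.04 to 10 × 0.10 × 0.442 = 0.44, where 0.442 = 0.409 + 0.033. A further 0.04 to 0.39 would get an onset after the visit. The loss of confirmation also requires that status is re-derived from dates. This is a cheap safeguard worth adding, not evidence that the results are wrong.

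**What to change.** In section 11.3.1, add for fever onset and first-symptom onset:

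> If the imputed date is after the first SDC visit or more than 30 days before it, or if the month is missing, the first SDC visit date is used. An imputed date does not determine early/late status: when the fever-onset date is partial, status follows the dengue acute panel for which the sample was scheduled (early-presenter panel, which includes dengue RT-qPCR, versus late-presenter panel). In the later-of rule in 6.1, an imputed date does not override a complete one.

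The text should refer to the dengue panel scheduled, not to any RT-qPCR result. Protocol Table 13 gives late presenters Zika and chikungunya RT-qPCR, and an NS1-positive early presenter without an RT-qPCR result must stay early. Where the recorded month precedes the visit month, the visit-date fallback can move an event to the visit month, so those cases should be listed.

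Reword section 11.2 to add 'except partial dates, see 11.3.1', and report the number of cases with a partial onset date. If there are none, one sentence saying so settles the matter.

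The cost is a few SAP sentences and a few lines of code, with no new data.
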